### Preliminary Studies

**VA Corporate Data Warehouse Review:** We determined we have significant sample to draw upon in VISN 20 to generate our retrospective cohorts. In a preliminary Corporate Data Warehouse, cross-sectional query of patients with PD seen in the PADRECC Movement Disorders Clinic, we discovered 477 living individuals with PD filled and were dispensed both a statin prescription and a LD prescription. Of those, 296 filled a prescription for a statin after starting LD. 181 PD patients filled a prescription for a statin prior to/around the time of an LD prescription fill. The largest group that was generated was the non-statin taking PD subjects filling a levodopa prescription to find matching characteristics from the VISN 20. This was substantial at nearly 900 patients (see Table 2). This information is important given that we will need 40 subjects in each of our 3 cohorts.

[figure not shown]
*Table 2. Feasibility of Generating Three Cohorts.*

Statin prior to Levodopa	Statin after LD	Total PD Patients with both LD and Statin	Non-statin PD patients using LD
181	296	477	900

**Clinical pilot data.** We obtained pilot data by inviting consecutive PD patients attending a clinic visit to be examined for the presence of dyskinesia. We reviewed by history and by VA pharmacy database records whether statins were prescribed before after or never in relationship to when the patient started L-Dopa. While this "spot" dyskinesia rating is easy to obtain, we confirmed that it is not very accurate compared with performing a levodopa-ON medication cycle (our study protocol involves a levodopa cycle). Out of 19 consecutive data collections, 6 were in levodopa-OFF states (one cannot express dyskinesia if OFF) usually because they forgot to take another dose of medication that day. We discovered that it's not uncommon for patients to take their first dose of medicine in the morning, but then forget to take subsequent doses on a busy day that involves coming to clinic in the afternoon! Of the remaining 13, we found that patient's memory of when they started levodopa and when they started a statin was accurate for most, and we found the pharmacy database to be very accurate and comprehensive.

Results of this small sample may suggest a trend towards more dyskinesia in the never treated group. (see Figure D) Of course, there is no adjustment for confounders like years of levodopa use etc. in this very preliminary dataset.

*Figure D. Clinical Pilot Data.*

**Force plate measured of Dyskinesia is Valid, Reliable, and Sensitive.** We have a unique method of measuring LID that is precise, reproducible, and sensitive to change. This is due to a combination of techniques. First, since the expression of dyskinesia is dependent on levodopa levels and the ON cycle, we use intravenous IV levodopa to create reliable motor ON cycles. This resource is unique to our center, as the use of IV levodopa for this purpose was pioneered by Director Emeritus [name] MD and he continues to hold the IND for IV levodopa (see Rationale for use of Levodopa below).

Second, we have an objective electronic instrument to measure dyskinesia. In our previous work funded by a VA Career Development Award, we determined that a force plate under the feet of a standing subject can quantify the severity of LID when used in subjects who undergo intravenous levodopa administration[23]. We noted that LID caused a unique appearance in the center of pressure (CoP) displacements in PD subjects. Upon inspection of over a dozen parameters quantifying CoP displacements during 30 seconds of stance with a secondary cognitive task, we found that the root mean square of the velocity in the anterior-posterior direction (RMSV) correlated extremely well with clinical LID rating scores (See

Figure E and Figure F).

Figure E. Forceplate CoP plots.

[figure not shown]
[figure not shown]

Figure F. Forceplate Measured Dyskinesia.

These results were developed using clinimetric standards, to measure LID successfully. Not only is the instrument objective because of the nature of instrumentation versus visual (human) ratings, it has proven to be more responsive to detecting changes in LID compared with a visual rating scale. Furthermore, we have shown the force plate to be more reliable under test-retest conditions than visual ratings.

We have demonstrated the effect size measured by the plate to be much larger than a visual rating scale of severity, so that a study utilizing the force plate will require only 41% of the subjects normally needed to demonstrate a change in LID compared with the current gold standard method of visual rating.

**Inertial sensor measured LID:** In the past decade, several attempts to establish an objective measurement of dyskinesia using accelerometers have been undertaken. Many of the studies have

been limited when distinguishing voluntary versus involuntary movement. A neural network approach (multiple sensors around the body), lend ot richer data on movement, most affected wrist, right, and left ankle. We will use these to measure gait characteristics, dyskinesia, tremor, and attempt to calculate "ON" and "OFF" time. We will use these to measure gait characteristics, dyskinesia, tremor, and attempt to calculate "ON" and "OFF" time. We will use these to measure gait characteristics, dyskinesia, tremor, and attempt to calculate "ON" and "OFF" time.

**Summary of Preliminary Data:** The database pull we secured demonstrates that we have an adequate patient sample base to derivate our three retrospective cohorts. We have sensitive and reliable methods for objectively measuring LID, ensuring that we are actually measuring the outcome we want to study. We have the infrastructure, tools, and the track record of successfully completing clinically relevant and demanding studies. We have a small preliminary prospective trial with a trend that supports the possibility of a statin effect in dyskinesia modulation. A one-look dyskinesia measurement protocol showed that subjects are often in motor states that are invalid for studying dyskinesia expression, confirming the need for an L-dopa cycle to accurately quantify dyskinesia in a standardized way. We are poised to determine if our basic scientists have uncovered a method of intervening with statins to delay the onset and therefore progression of the inevitable worsening in severity of LID.

### Specific Aims

**Aim 1. Statin Use & LID Development:** Determine if statin use coincident (prior) to LD initiation reduced LID development compared with no statin use or late statin use using a retrospective cohort design.

*Hypothesis 1:* HMG-CoA reductase inhibition by statin interrupts the molecular signaling changes induced by LD in the earliest period of exposure associated with "priming" for LID.

**Aim 2 Statin Use & LID Severity:** Determine if statin use after LD is initiated reduced LID development (severity) over time compared with no statin use using a retrospective cohort design.

*Hypothesis 2:* HMG-CoA reductase inhibition by a statin can still be effective in reducing the development of progression of dyskinesia even if started after priming processes are established.

**Aim 3 LID and pERK1/2:** Determine levels of phosphorylated ERK1/2 levels in CD3/CD20 lymphocytes and compare them with dyskinesia severity.

*Hypothesis 3:* Dyskinesia severity correlates with phosphorylated ERK1/2 levels and may associate as a dyskinesia biomarker.

**Aim 4 LID Measurement:** Compare the dyskinesia measurements between the force plate, the inertial sensors, the Unified Dyskinesia Rating Scale (UDysRS), and the Modified Abnormal Involuntary Movement Scale (mAIMS).

*Hypothesis 4:* The force plate is a valid and reliable method of measuring dyskinesia when compared to the gold standard (mAIMS), a patient/clinician impression of dyskinesia (UDysRS), and a novel form of dyskinesia measurement (the inertial sensors).

### Research Design and Methods

**Overview:** This study is a retrospective three cohort design and will compare statin exposure BEFORE beginning LD, *versus* statin exposure AFTER LD is begun, *versus* NO statin exposure in PD subjects who

are matched for disease characteristics (severity), gender, and total LD exposure. The primary endpoint is the severity of LID between the groups after years of opportunity to develop LID. The power of the VA database is its ability to identify the subjects appropriate for our three cohorts. Dyskinesia amplitude will be measured repeatedly over a single intravenous levodopa cycle, generating an area under the curve (AUC) for each subject, leading to a group AUC for each cohort. All dyskinesia ratings will be by a blinded rater. We will be able to determine whether a statin reduces eventual LID in Veterans who take levodopa for PD, an important public health problem that causes quality of life reduction and raises health care costs for the Veterans Health Administration.

[figure not shown]
**Primary Endpoint:** Difference between cohorts in peak Unified Dyskinesia Rating Scale

**Secondary Endpoints:** Difference between cohorts in AUC of RMSV-AP through levodopa cycle, AUC mAIMS of LID through levodopa cycle

**Tertiary Endpoints:** QoL scales (PDQ-39, PDys-26,) and ERK1/2 levels as correlated with AUC RMSV – AP through levodopa cycle in subjects

**Rationale for study population:** We will generate three retrospective cohorts: (Cohort A) Statin Exposure before LD, (Cohort B) Statin Exposure after LD, and (Cohort C) No statin exposure (or LD only). See Figure F.

*Figure G. Study Design.*

We will also perform a subgroup analysis comparing simvastatin  $\leq 20$ mg/day (low dose) and a high dose group  $\leq 80$  mg/day.

**Rationale for Dyskinesia endpoints:** We are measuring LID with (A) Unified Dyskinesia Rating Scale, (B) Force Plate, and (C) Subjective Measures.

A. Unified Dyskinesia Rating Scale (UDysRS): The Movement Disorders Society has adopted this scale as the recommended primary measurement tool for dyskinesia. It was determined be best amongst many existing scales to detect changes in dyskinesia using a known treatment that reduces LID severity[24].

B. Force Plate: We have developed a highly *objective* mechanized method of measuring dyskinesia compared to the current gold standard method, which otherwise involves patient *subjective* ratings and observer visual rating scales which are subject to bias and imprecision. (VA Career Development Award)[23].

C. Subjective Measures: Parkinson's Dyskinesia Scale (PDys-26) is a means of assessing the impact of dyskinesia on aspects of everyday living, a quality of life scale[25].

**Rationale for the Intravenous Levodopa Cycle:** While this method is more intensive for subjects and researchers, it has been one of the best means of studying pharmacokinetics/dynamics of LD and dyskinesia for over 25 years. This system controls many variables that would otherwise widen confidence intervals and require an order of magnitude more subjects to observe significant effects.

The purpose of the IV LD cycle is to control a variable that can alter the moment to moment expression of levodopa-induced dyskinesia (LID)--the degree of the motor ON state the subject is experiencing. The "ON" state is dependent on brain LD levels, which are in turn dependent on plasma LD levels (LD is transported into the brain via a low molecular weight amino acid transporter, competing with other amino acids), thus LID expression is overwhelmingly dependent on LD plasma (and brain) levels. Intestinal absorption of oral LD can be erratic and this variability can introduce unacceptable variability in LID. Secondly, with high protein food intake (in our protocol, protein intake is controlled during the study day), excessive competition for transport of levodopa into the brain can reduce the ON motor state. For these 2 reasons, IV levodopa is a far more controlled way to ensure similar motor conditions that underpin expression of LID.

**Rationale for measuring a whole levodopa cycle:** Repeated measurements throughout a 6-hour testing period to create an area under the curve (AUC) metric minimizes the impact of erratic outlying single measures. Most importantly though, calculating an AUC after observing a whole levodopa cycle is intuitively superior to single measurements in time, especially when comparing dyskinesia over separate visits. For example, if a one-time LID score was taken and the subject's levodopa level was not at the peak level of the cycle, yet at the next study visit, the LID score was taken at a good peak levodopa moment, the score could be quite different. This normal variability could overwhelm any effect of an anti-dyskinetic intervention. This is controlled best with an identical dose IV levodopa infusion with repeated dyskinesia measurements during several hours of testing.

1.5 mg/kg/h for 2 hours was chosen for the infusion rate as it consistently produces the motor ON state. This has been established from a 25+ year experience performing infusion studies at our Clinical Translational Research Center. In a review of papers from other centers using LD infusions, no reports of adverse events (AEs) were recorded.[26][27][28] A review of IV LD in PD concluded that this methodology was safe and effective.[29] One report of nausea in subjects receiving IV LD was published by Black et al[30], however in that protocol, subjects received at least 4.5 mg/min loading doses of LD (i.e. over 10 minutes). In IV LD studies at our center, we do not use loading doses, only constant rate infusions. For example, in a 70-kg subject, a 1.5 mg/kg/hr. rate infuses 1.75 mg/minute for the duration of the infusion, a 60% less concentrated amount. Our University site investigator ([name]) has held an IND for intravenous LD for over 2 decades and one serious AE has been recorded. This serious AE involved overnight hospitalization after a syncopal episode during the second hour of the IV infusion. The IV infusion was immediately discontinued and no sequela occurred. Nausea has rarely been reported by subjects at our center. Based upon nearly 30 years of experience, we have found this method to be easy to administer and easy on subjects. In our pilot study of DHA for prevention of dyskinesia, we have administered over 150 levodopa infusions in the last 4 years, and no serious AEs have occurred.

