**Exclusion Criteria:**

- Deep Brain stimulation
- Unable to stand for 1 minute intervals, or sensory deficits in the feet
- Significant cognitive impairment as measured by the Montreal Cognitive Assessment score of < 16
- Subjects with unstable medical or psychiatric conditions (including hallucinations).
- History of unstable medical conditions (i.e. active cardiac disease, recent unwellness, surgery etc.)
- Current use of drugs that may affect parkinsonism or dyskinesia: dopamine receptor blocking medications, depakote, lithium, amiodarone, tetrabenazine, metoclopramide, dronabinol, and illicit drugs such as marijuana (THC), cocaine, methamphetamine
- Unwilling to hold amantadine (if taking) for 24 hours prior to the day-patient visit)

**Cohort Generation:** Recruitment will occur that patients who come to clinic will be approached for interest in participating as they attend in temporal order and fulfill minimal inclusion/exclusion criterion. We will avoid matching as that can introduce bias. Adjustments for differences in baseline characteristics will be made during data analysis including disease duration, levodopa equivalents, age. Gender is likely to be well matched (male) given the nature of the Veteran population.

Given recruitment demands and studying the evidence for excluding certain statin types our conclusion is that to meet a vigorous recruiting goal successfully, the inclusion of all statins would be beneficial, and unlikely to confound the results of our study.

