### Data Analysis.

The peak UDysRS total score will be used as the primary outcome measurement for LID as it is the accepted gold standard. We believe a more sensitive, precise, and reliable measure is our method of AUC calculations with IV levodopa, a full motor ON cycle and the use of an electronic measuring instrument (force plate). Therefore, additional outcome measurements will involve the computation of area under the curve for LID measurements of Modified Abnormal Involuntary Movement Scale (mAIMS) and the forceplate root mean square velocity in the anterior-posterior direction will be computed using the trapezoidal rule.

[figure not shown]
Primary analysis will follow a per protocol framework, using ordinary least-squares (OLS) regression to examine the difference between the groups (statin before LD, LD before statin, LD without statin) on LID outcome measures while correcting for LID related co-variates. Due to the nature of the retrospective selection, care will be taken to statistically account for potential confounders and modifiers on the relationship between LID and statin use. These will include, but not be limited to, age at onset of PD, gender, length of time taking L-dopa, total daily L-dopa dose, duration of disease, disease severity, and the presence of non PD factors related to a statin such as hypertension. In order to evaluate potential influences of secondary, cerebrovascular effects of indicated statin use on LID as an additional exploratory aim, we will also assess both duration (as a continuous linear variable) and dose of simvastatin (low dose  $\leq 20$ mg/day and a high dose group  $\leq 80$  mg/day) on changes in LID. Secondary outcomes will include examination for treatment group differences in changes in Parkinsonism (tapping AUC, UPDRS III, Hoehn and Yahr, Schwab and England, PDQ-39) including pERK1/2 levels following the previously described methods. Should violations of normal regression assumptions be found, either outcome transformations or alternative regression distributions (e.g. negative binomial to account for positive skew) will be applied as necessary. Sub analyses will examine co-morbidity rates between the groups.

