Additionally, pERK1/2 levels will be examined. Initial analysis will examine the relationship between severity of dyskinesia (with the AUC of the RMSV) and pERK1/2 levels using correlations. Further analysis will examine if pERK1/2 levels vary by cohort using ANOVAs and multiple regression techniques. Assessment of confounders of the relationship between pERK1/2 and dyskinesia severity will be examined.

**Sample Size:** Based on results of a validation study of dyskinesia scales [35], using a one-way ANOVA to examine the difference in part 3, impairment, of the Unified Dyskinesia Rating Scale (UDysRS) between the three pairwise comparisons, 37 participants are needed in each group to detect a moderate effect size ( $f=0.30$ , at least one group difference of 3.75 points) with a significance of 0.05 and power of 0.80. Pairwise comparison of statin before levodopa versus no statin will receive priority. To account for drop outs, an additional 3 participants will be included in each of the groups. Additional 10 will be included for screen failures (total 130). Total enrollment will be 40 per group, 120 total. See Table 5 for estimated recruitment goals.

*Table 5. Estimated Recruitment Totals per Site*

	VAPORHCS	VAPUGHCS	OHSU	Total
Recruitment	60	28	32	120

*Figure 1. Recruitment Goals over time*

Subjects were described previously and in the first cohort will be those who had been on a statin first and remained on it while they were initiated on LD. The second cohort will be those who started a statin AFTER beginning LD. The third cohort will be subjects with no history of statin intake. Matching will occur based on gender, severity of disease based on a PD rating scale, and LD dose

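### The exploratory simvastatin dose bands overlap, and statins other than simvastatin have no dose rule although all statins are enrolled

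*Combined protocol and SAP*

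**What the plan says.** Three places in the combined protocol and SAP bear on this.

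- **Research Design and Methods, rationale for study population.** "We will also perform a subgroup analysis comparing simvastatin" at no more than 20 mg/day with a second group, worded as "low dose) and a high dose group $\leq 80$ mg/day". No lower limit is given for the second group.
- **Data Analysis.** The same two limits appear again: "we will also assess both duration (as a continuous linear variable) and dose of simvastatin". The sentence describes this as an evaluation of "effects of indicated statin use on LID as an additional exploratory aim".
- **Exclusion Criteria, Cohort Generation paragraph.** Eligibility is not restricted by statin type: "the inclusion of all statins would be beneficial, and unlikely to confound the results of our study".

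No section gives a dose category or an equivalence rule for a statin other than simvastatin. Hypotheses 1 and 2 in Specific Aims are framed for statins as a class. The inclusion criteria require Cohort A to be on a statin throughout levodopa treatment and allow interrupted use in Cohort B.

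**The concern.** A low-versus-high comparison needs groups that exclude each other. As worded, the low group sits wholly inside the high group, and the wording occurs in both the design and the analysis text, so it does not look like an isolated slip. An analyst must either follow the text and obtain a diluted contrast, or supply a lower limit that the plan does not state.

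The second gap is coverage. Cohorts A and B may contain users of any statin, but the dose rule applies to simvastatin alone. The others are left out, or a rule for them is devised once the data are in hand.

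This is the one place where the Data Analysis section relates dose or duration among statin users to dyskinesia. Exposure is not randomised, so readers will look here for a gradient. A diluted contrast could wrongly suggest there is none, and an undefined one leaves room for choices made after the results are seen.

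**Working it through.** **Inputs from the documents.** Dose limits of 20 and 80 mg/day (study population rationale; Data Analysis). From Sample Size: 37 evaluable and 40 enrolled per group, f = 0.30, a 3.75-point difference, significance 0.05, power 0.80. Cohorts A and B together therefore hold 2 × 37 = 74 evaluable or 2 × 40 = 80 enrolled statin users.

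**Assumed, because the documents do not give them.** The low-dose share q of simvastatin users, the simvastatin share s of statin users, and the true standardised dose difference d.

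**Step 1: the plan's own figure.** One-way ANOVA, 3 groups, noncentral F with λ = N·f². At 37 per group, N = 111 and λ = 111 × 0.09 = 9.99, giving power 0.8035. At 36 per group power is 0.7916. So 37 is reproduced, 37 + 3 = 40, and 3 × 40 = 120. None of this uses the dose bands. No size or power is stated for the dose analysis.

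**Step 2: the bands.** Any dose of 20 mg/day or less is also 80 mg/day or less, so the low set is contained in the high set.

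**Step 3: effect on the contrast.** Let μL be the mean at 20 mg/day or less and μH the mean above 20 and up to 80. The literal high group has mean q·μL + (1 − q)·μH, so

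literal high mean − low mean = (1 − q)(μH − μL).

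| q (assumed) | share of true difference kept | attenuation |
|---|---|---|
| 0.3 | 0.70 | 30% |
| 0.5 | 0.50 | 50% |
| 0.6 | 0.40 | 60% |

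**Step 4: effect on the test.** Take 80 simvastatin users, q = 0.5 and unit SD (all assumed).

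- SE used by an ordinary two-sample test: √(1/80 + 1/40) = 0.194.
- Actual SE of the literal contrast: (1 − q)·√(1/40 + 1/40) = 0.5 × 0.224 = 0.112.
- Critical difference: about 1.98 × 0.194 = 0.383, or 0.383/0.112 ≈ 3.4 actual SEs. The two-sided null rejection rate is then about 0.0006 against a nominal 0.05.

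A simulation of 10,000 runs agrees:

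| true d | rejection, literal groups | rejection, disjoint groups (40/40) |
|---|---|---|
| 0 | 0.0006 | 0.05 |
| 0.50 | 0.10 | 0.60 |
| 0.735 | 0.38 | 0.90 |

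The value 0.735 is the plan's 3.75 points on its implied SD if the three cohort means are evenly spaced: SD of means 3.75 × √(1/6) = 1.531, residual SD 1.531/0.30 = 5.10, and 3.75/5.10 = 0.735. It is a reference value, not a dose effect stated by the plan.

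**Step 5: simvastatin only.** With s = 0.3 to 0.6 (assumed), 74 × 0.3 ≈ 22 to 74 × 0.6 ≈ 44 users enter the dose analysis. For the same SD and low/high split, the SE relative to using all 74 is 1/√0.3 = 1.83 to 1/√0.6 = 1.29. With disjoint bands and d = 0.50, power is 0.60 for 40 versus 40 and 0.34 for 20 versus 20. The restriction changes precision and the population described; it does not shift the low-versus-high difference among simvastatin users.

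**Step 6: duration.** It enters as a continuous linear term, so the bands play no part in it. What is open is whether the words after *dose* (of simvastatin) also govern *duration*, and, since Cohort B use may be interrupted, whether duration is elapsed or cumulative.

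**The case against.** The strongest reply is that the labels show the intent: one group is low, the other high, they are to be compared, and any competent analyst would start the second band above the first. On that view a lower limit was simply omitted and the attenuation never arises. Part of this stands. The 30–60% depends on forming the groups literally and comparing their means; two nested indicators in one regression, for example, would recover the full low-versus-high difference. But that makes the result depend on an unstated choice, and the rule that is stated, in both places, is the overlapping one.

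It can also be said that staying with one molecule avoids approximate potency conversion. That is a defensible trade-off, and simvastatin-only deserves to remain as a sensitivity analysis. The plan does not present it as a deliberate choice, however, and it sits beside a paragraph opening enrolment to all statins.

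Four stronger readings are tempting, and the documents do not support them:

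- **The overlap distorts the duration analysis.** It does not; duration is a continuous term.
- **The simvastatin restriction biases the dose contrast.** It reduces numbers and generality only.
- **Most exposure data are discarded.** The simvastatin share is not given; at an assumed 60%, 44 of 74 users are kept.
- **The main result is at risk.** The analysis is labelled exploratory, and the cohort comparison does not use the bands.

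**Conclusion.** The point holds in limited form. The two dose bands are not mutually exclusive in either place where they are defined. Applied literally, the comparison estimates (1 − q) of the true difference, and an ordinary two-sample test on overlapping groups is far too conservative: about 0.0006 instead of 0.05 under the null for 80 users and q = 0.5. These sizes rest on assumed values of q, since the documents give no dose distribution.

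Separately, users of statins other than simvastatin have no place in the dose analysis, a loss of precision of roughly 1.3 to 1.8 times in the SE under an assumed simvastatin share of 30–60%. The scope of duration is undefined.

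The primary comparison and the 37 evaluable and 40 enrolled per group are unaffected. The correction should be made because a stated analysis rule is wrong as written and costs almost nothing to repair; it is not critical to the study's main conclusion.

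**What to change.** Reconcile the study population rationale, the Cohort Generation paragraph and the Data Analysis section, before the dose data are examined:

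1. Make the analysis bands disjoint, with the high band starting where the low band ends. The sponsor should confirm the cut-off. This concerns analysis categories only, not treatment.
2. Define duration as cumulative time on any statin, analysed over all statin users.
3. State in advance one rule for placing other statins in the dose analysis, for example a single dose-equivalence table, including how a change of statin or dose is handled.
4. Keep simvastatin-only as a sensitivity analysis.

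Dividing statin-years by levodopa-years is not a good substitute for item 2. By the cohort definitions the ratio is at least 1 in Cohort A and below 1 in Cohort B, so it largely repeats the cohort contrast.

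The cost is SAP wording and one table. The screening and day-visit procedures already ask about past statin use and obtain outside medication histories; the team should confirm that the forms record statin, dose, and start and stop dates. The downside is that potency equivalence is approximate, which the simvastatin-only sensitivity analysis addresses.
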